6.1.4.2. Sensitivity/Supplementary Analysis

Not applicable.

6.2. Secondary Endpoints

6.2.1. Immunogenicity Endpoints

6.2.1.1. Main Analysis

- Estimands: All immunogenicity estimands (including seroconversion/seropositive percentages, GMTs, and GMFRs) for secondary endpoints (Section 2.2).
- Analysis set: Evaluable immunogenicity population (Section 4).

- Analysis time point: At each blood sampling time point (at baseline, 4 weeks after vaccination). GMFRs, seroconversion percentages, and seroresponse percentages can only be reported out for postvaccination time points (Section 3.2).
- Analysis methodology: Descriptive statistics including 95% CIs as per Section 5.2.
- Intercurrent events and missing data: Antibody titers below the LLOQ will be treated as specified in Section 5.3. Missing data will not be imputed.
- Reporting results:

Influenza:

- Descriptive statistics, including the sample size (n), HAI GMTs, GMFRs, and 95% CI for the HAI GMTs and GMFRs, will be presented for each strain by study intervention group.
- The proportion of participants achieving HAI seroconversion and the associated 2-sided Clopper-Pearson 95% CIs will be provided for each strain by study intervention group.
- The proportion of participants with HAI titers ≥1:40 and the associated 2-sided Clopper-Pearson 95% CIs will be provided for each strain by study intervention group.
- Seroconversion proportions, GMTs, and GMFRs may be plotted by study intervention group.

SARS-CoV-2:

- The SARS-CoV-2 GMT, GMFRs, and the proportion of participants with seroresponse will be estimated for each strain by study intervention group.
- Seroresponse proportions, GMTs, and GMFRs may be plotted by study intervention group.

6.2.1.2. Sensitivity/Supplementary Analysis

- Empirical RCDCs with HAI titers and SARS-CoV-2—neutralizing titers will be plotted separately for each strain by study intervention group.
- Additional analyses may be performed based on the mITT population if there is a large enough difference (>10%) in sample size between the mITT population and the evaluable immunogenicity population.

- The difference in the proportion of participants achieving HAI seroconversion between each study intervention group and comparator group (Group 1 and Group 12) at 4 weeks after vaccination will be provided for each strain.
- The difference in the proportion of participants achieving SARS-CoV-2 seroresponse between each study intervention group and the comparator group (Group 1) at 4 weeks after vaccination will be provided for each strain.
- The unadjusted and baseline titer—adjusted GMR of strain-specific HAI titers between each study intervention group and comparator group (Group 1 and Group 12) at 4 weeks after vaccination will be provided for each strain.
- The unadjusted and baseline titers—adjusted GMR of SARS-CoV-2—neutralizing titers between each study intervention group and the comparator group (Group 1) at 4 weeks after vaccination will be provided for each strain.

6.3. Subset Analyses

Subgroup analyses based on baseline SARS-CoV-2 infection status will be performed for the secondary SARS-CoV-2 immunogenicity endpoints, by study intervention group. Subgroup analyses based on baseline HAI titer value will be performed for the HAI seroconversion endpoint. No subset analyses are planned by sex, race, or ethnicity.

6.4. Baseline and Other Summaries and Analyses

6.4.1. Tertiary/Exploratory Endpoints

The exploratory endpoints in Section 3.3 may be summarized using the same populations and methods as for the secondary endpoints:

- SARS-CoV-2 VOC GMTs and the associated 95% CIs will be provided for VOCs not already specified, by study intervention group, for participants 18 through 64 years of age.
- SARS-CoV-2 VOC GMFRs from before vaccination to each time point after vaccination, and the associated 95% CIs, will be provided for VOCs not already specified, by study intervention group, for participants 18 through 64 years of age.
- SARS-CoV-2 VOC seroresponses at each time point after vaccination, and the associated 95% CIs, will be provided for VOCs not already specified, by study intervention group, for participants 18 through 64 years of age.

In addition, the participants who reported at least 1 symptom indicative of myocarditis or pericarditis within 4 weeks after vaccination will be summarized descriptively.

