8.4.7. Adverse Events of Special Interest

The following events are considered AESIs:

For Substudy A:

- A confirmed diagnosis of influenza.
- Confirmed diagnosis of myocarditis or pericarditis occurring within 4 weeks after vaccination. See Section 10.11.8.8.10.
- Confirmed COVID-19 diagnosis after Visit 1 through the end of the study (clinical signs/symptoms per CDC²⁸ and positive SARS-CoV-2 NAAT or rapid antigen test result).

For Substudy B:

- A confirmed diagnosis of influenza.
- Confirmed diagnosis of myocarditis or pericarditis occurring within 6 weeks after vaccination. See Section 10.12.8.12.
- Confirmed COVID-19 diagnosis after Visit 201 through the end of the study (clinical signs/symptoms per CDC²⁸ and positive SARS-CoV-2 NAAT or rapid antigen test result) (excluding Group 12).
- Potential menstrual cycle disturbances. See Section 10.12.8.11.

AESIs are examined as part of routine safety data review procedures throughout the clinical trial and as part of signal detection processes. Should an aggregate analysis indicate that these prespecified events occur more frequently than expected, eg, based on epidemiological data, literature, or other data, then this will be submitted and reported in accordance with Pfizer's safety reporting requirements. Aggregate analyses of safety data will be performed on a regular basis per internal SOPs.

All AESIs must be reported as an AE or SAE following the procedures described in Section 8.4.1 through 8.4.4. An AESI is to be recorded as an AE or SAE on the CRF. In addition, an AESI that is also an SAE must be reported using the Vaccine SAE Report Form.

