	In participants 18 through 64 years of age complying with the key protocol criteria (evaluable participants): GMTs before vaccination and at each blood sampling time point after vaccination for each strain GMFR from before SARS-CoV-2 vaccination to each blood sampling time point after SARS-CoV-2 vaccination for each strain Percentages of participants with seroresponse ^c at each blood sampling time point after SARS-CoV-2 vaccination for each strain	SARS-CoV-2 neutralizing titers by strain
Tertiary/Exploratory	Tertiary/Exploratory	Tertiary/Exploratory
To describe the immune response to emerging variants (under monitoring, of interest, and/or of concern) in participants 18 through 64 years of age	As detailed in the SAP	SARS-CoV-2 neutralizing titers for variants (under monitoring, of interest, and/or of concern)
To describe the troponin and ECG abnormalities detected in participants who are evaluated for possible cardiac symptoms	As detailed in the SAP	Troponin I laboratory parameters detailed in Section 10.2 ECG abnormalities consistent with probable or possible myocarditis or pericarditis as defined in Section 10.12.8.5.1

- There are no primary immunogenicity objectives in this study.
- b. Seroconversion is defined as an HAI titer <1:10 prior to vaccination and ≥1:40 at the time point of interest, or an HAI titer of ≥1:10 prior to vaccination with at least a 4-fold rise at the time point of interest.

- c. Seroresponse is defined as achieving a ≥4-fold rise from baseline (before the study vaccination). If the baseline measurement is below the LLOQ, the postvaccination measure of ≥4 × LLOQ is considered seroresponse.

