- Assess systemic events (if present) in accordance with the grades provided in Section 8.3.5.3.

- Assess other findings associated with the reaction and record this on the AE page of the CRF if appropriate.
- The investigator or an authorized designee will complete the unscheduled visit assessment page of the CRF.

10.12.8.10. Additional Procedures for Monitoring of Potential Myocarditis or Pericarditis for Substudy B

Any study participant who reports acute chest pain, shortness of breath, palpitations, or any other symptom(s) that might be indicative of myocarditis or pericarditis within 6 weeks after study vaccination must be specifically evaluated in clinic by a cardiologist for possible myocarditis or pericarditis. The same applies for any participant in whom a new ECG abnormality (compared to baseline) consistent with probable or possible myocarditis or pericarditis (as listed in Section 10.12.8.5.1) or abnormal troponin I level is observed at Visit 202 or Visit 203.

In addition to a clinical evaluation, the following should be performed:

- ECG and
- Measurement of the troponin level

For any participant in whom a new ECG abnormality (compared to baseline) consistent with probable or possible myocarditis or pericarditis (as listed in Section 10.12.8.5.1) or abnormal troponin I level is observed at Visit 202 or Visit 203, this should be achieved by repeating the assessments with the central vendor(s).

If myocarditis or pericarditis is suspected based upon the initial evaluation, the following should also be performed:

- Cardiac echocardiogram and/or
- Cardiac magnetic resonance study

Details of the symptoms reported, and results of the investigations performed, will be recorded in the CRF.

Any diagnosis of myocarditis or pericarditis is considered an important medical event and must be reported as an SAE (refer to Sections 8.4.1.1 and 8.4.3). Other diagnoses should be recorded as AEs or SAEs, as appropriate. Refer also to Section 8.4.7.

10.12.8.11. Additional Procedures for Monitoring of Potential Menstrual Cycle Disturbances for Substudy B

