- Assess for other findings associated with the reaction and record these on the AE page of the CRF if appropriate.
- The investigator or an authorized designee will complete the unscheduled visit assessment page of the CRF.

10.12.8.12. Additional Procedures for Monitoring of Potential Myocarditis or Pericarditis for Substudy B

During Substudy B, participants 18 through 64 years of age will be closely monitored for potential asymptomatic and symptomatic myocarditis/pericarditis, including the use of routine ECGs and troponin testing.

Any study participant who reports acute chest pain, shortness of breath, palpitations, or any other symptom(s) that might be indicative of myocarditis or pericarditis within 6 weeks after study vaccination must be specifically evaluated in clinic by a cardiologist for possible myocarditis or pericarditis:

- Acute chest pain,
- Shortness of breath,
- Palpitations, or
- Any other symptom(s) that might be indicative of myocarditis or pericarditis.
- In addition to a clinical evaluation, the following should be performed:
- ECG and
- Measurement of the troponin level.

If myocarditis or pericarditis is suspected based upon the initial evaluation, the following should also be performed:

- Cardiac echocardiogram and/or
- Cardiac magnetic resonance study.

Details of the symptoms reported, and results of the investigations performed, will be recorded in the CRF. Any diagnosis made (eg, myocarditis, pericarditis, or other) should be recorded as an AE or SAE, as appropriate. Refer also to Section 8.4.7.

10.12.8.13. Additional Procedures for Monitoring of Potential Menstrual Cycle Disturbances for Substudy B

Any female study participant who reports any symptoms that may indicate a disturbance of their normal menstrual cycle (including, but not exclusively, heavy menstrual bleeding, amenorrhea, and irregular periods) following receipt of study intervention until 6 months after the first vaccination should be specifically evaluated by the investigator at the next planned visit. Details of the symptoms, menstrual history, and results of any investigations performed will be recorded in the CRF.

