10.12.9.3.5. Other Safety Analyses for Substudy B

The data collected for study participants who report any symptom(s) that might be indicative of myocarditis or pericarditis within 4 weeks after a study vaccination (ECG, troponin level, cardiac echocardiogram, and/or cardiac magnetic resonance study) will be summarized and listed by study intervention.

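### Substudy B mandates cardiac evaluation of symptoms within 6 weeks of vaccination, but the committed summaries of those evaluations cover only symptoms within 4 weeks

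*SAP*

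**What the plan says.** **Evaluation and data capture (Protocol).** Sections 10.12.8.10 and 10.12.8.12 cover participants in Substudy B who report chest pain, shortness of breath, palpitations or other symptoms "indicative of myocarditis or pericarditis within 6 weeks after study vaccination must be specifically evaluated in clinic by a cardiologist". An ECG and a troponin measurement are required, with echocardiogram and/or cardiac MR if the suspicion persists. Both sections then say: "Details of the symptoms reported, and results of the investigations performed, will be recorded in the CRF". Section 8.4.7 lists as an AESI for Substudy B: "Confirmed diagnosis of myocarditis or pericarditis occurring within 6 weeks after vaccination".

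**Objective.** Protocol 10.12.3 and SAP B 2.2 include an exploratory objective: "To describe the troponin and ECG abnormalities detected in participants who are evaluated for possible cardiac symptoms". It carries no time limit.

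**Committed analyses.** There are two outputs, described in three places.

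- Protocol 10.12.9.3.5 and SAP B 6.5 commit to summarizing and listing, by study intervention, the ECG, troponin, echocardiogram and MR data of participants reporting symptoms "indicative of myocarditis or pericarditis within 4 weeks after a study vaccination".
- SAP B 6.4.1 adds: "In addition, the participants who reported at least 1 symptom indicative of myocarditis or pericarditis within 4 weeks after vaccination will be summarized descriptively". This sentence names neither vaccine group nor ECG, troponin or imaging data. The commitment by group therefore rests on Protocol 10.12.9.3.5 and SAP B 6.5.

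**The concern.** The protocol requires a work-up for every suggestive symptom up to 6 weeks and stores the result, but the only committed analyses of symptom-triggered work-ups select on symptoms up to 4 weeks. A program written exactly to the plan would leave out some evaluations that the protocol itself made mandatory.

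What is at stake is the reader's ability to see, by vaccine group, how many late suspected events were investigated and what the tests showed. That matters most for suspected events that end in no diagnosis or a nonserious one, because they have no other route into a table.

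**Working it through.** The plan gives no figure to reproduce here. The check compares the stated windows and then looks for any other committed output that would close the gap.

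**Windows**

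| Item | Source | Window |
|---|---|---|
| Mandatory evaluation of symptoms | Protocol 10.12.8.10, 10.12.8.12 | 6 weeks = 6 × 7 = 42 days |
| AESI, myocarditis/pericarditis | Protocol 8.4.7 | 6 weeks |
| Summary and listing of work-up data, by group | Protocol 10.12.9.3.5, SAP B 6.5 | 4 weeks = 4 × 7 = 28 days |
| Descriptive summary of participants | SAP B 6.4.1 | 4 weeks |

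Uncovered interval: 42 − 28 = 14 days, and 14/42 = 33%. If 4 weeks is read as the Visit 204 window (days 26 to 30, Protocol 10.12.8.9.5), the interval is 42 − 30 = 12 days to 42 − 26 = 16 days, or 29% to 38%. These are shares of calendar time in the evaluation window, not shares of risk.

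The summaries are keyed to when the symptom was reported. A late test for a symptom reported by week 4 is therefore still included. The gap concerns symptoms first reported after week 4 and up to week 6.

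**Could another committed output show these work-ups?**

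- Primary troponin and ECG analyses (SAP B 6.1.3.1, 6.1.4.1) use only the day 2 to 4 and day 6 to 8 visit windows, so later unscheduled tests fall outside them.
- The AE table by vaccine group stops at 4 weeks (SAP B 6.1.2.1).
- The SAE table by vaccine group runs to 6 months (SAP B 6.1.2.1). It shows any diagnosis reported as an SAE, but not a work-up that ended without one.
- AEs within 48 hours of the Visit 204 blood draw are summarized or listed (SAP B 6.1.2.2). This reaches day 32 at most (30 + 2), no vaccine group is stated, and it would show an event rather than test results.
- SAP B commits to no AESI table. Summaries by type of AE are optional (SAP B 6.1.2.2), as are extra troponin and ECG summaries (Protocol 10.12.9.3.4).
- SAP B 2.2 refers the exploratory objective to its Section 3, but Section 3.3 lists only variant titers, so nothing there sets a different window.

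None of these closes the gap. With the three sentences set to 6 weeks, the uncovered interval falls from 14 days to 0.

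**The case against.** The strongest reply is that little is lost.

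- Protocol 10.12.8.10 says: "Any diagnosis of myocarditis or pericarditis is considered an important medical event and must be reported as an SAE". Such a diagnosis in weeks 5 or 6 would be in the SAE table by group. This stands. Because 10.12.8.12 is less firm ("Any diagnosis made (eg, myocarditis, pericarditis, or other) should be recorded as an AE or SAE, as appropriate"), the reassurance is best limited to diagnoses actually reported as SAEs.
- Protocol 2.3.1 says cases have typically occurred within 14 days of vaccination, so few are expected after week 4. This stands, and limits the size of the effect.
- AESIs are examined in routine safety review (Protocol 8.4.7). That is monitoring, not a committed display in the report.
- The protocol's analysis row for the exploratory objective is optional (10.12.9.3.4). A reader might infer that a promised objective goes unmet. The documents do not support that, because no complete display was promised. The point rests on the mismatch between the mandated evaluation and the summaries that are committed.
- Four weeks matches other Substudy B safety windows, such as the AE tables and the stopping rules (Protocol 10.12.8.7). A reader might infer that 4 weeks is simply left over from before the AESI window was lengthened in Amendment 5. The sequence of versions allows that reading but does not establish it, and the point does not need it.
- Not every participant need have been under a 6-week mandate. Note b to the Substudy B schema (Protocol 1.2) says Groups 1, 3, 4 and 5 enrolled under a prior protocol version. At planned numbers that is 30 + 3 × 120 = 390 of 630. The amendment history dates the 6-week AESI window to Amendment 5, and the documents do not say which prior version applied. This stands and shapes the fix.
- One pooled 6-week row would mix periods with different ascertainment. This also stands.

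**Conclusion.** The mismatch is real in the current text. With 4 weeks as day 28, one third of the mandated evaluation window (14 of 42 days) lies outside the committed summaries. Work-ups for symptoms first reported in that interval, and not reported as an SAE, have no committed display by vaccine group.

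The effect is limited to exploratory and other-safety descriptive output. No primary or secondary endpoint changes. A reader might infer that myocarditis or pericarditis cases would go unreported; the SAE table through 6 months argues against that for diagnoses reported as SAEs.

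A reader might also want an expected number of omitted work-ups among 630 participants. The documents give no rate of late symptom reports and do not establish that all 630 were under a 6-week mandate, so no such number is offered.

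The conclusion assumes that the analysis text will be applied as written. It is worth correcting because the correction is cheap and changes what a stated output contains.

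**What to change.** Change the analysis window from 4 to 6 weeks in Protocol 10.12.9.3.5 and in SAP B 6.5 and 6.4.1, so that the summaries match the evaluation window already in the protocol. Within those outputs:

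- show symptoms up to 4 weeks, and after 4 and up to 6 weeks, as separate rows;
- footnote that reports after Visit 204 are participant-initiated: Visits 201 to 203 tell participants to contact the site about cardiac symptoms, the Visit 204 list does not repeat this, and the next contact is the 6-month call;
- state which groups, if any, were enrolled under a protocol version without a 6-week mandate.

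The cost is a wording change in three places for two outputs, one extra row, a footnote and a statement on groups. The work-up results are already recorded in the CRF, so no new data collection is needed. The small downside is less complete ascertainment in the later row, which the separate row and the footnote make visible.

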6.4.2. Baseline Summaries

Descriptive summary statistics for demographic characteristics and medical history of SARS-CoV-2 will be generated by study intervention group, for participants 18 through 64 years of age, based on the safety population.

Each reported medical history term will be mapped to a SOC and PT according to MedDRA.

6.4.3. Study Conduct and Participant Disposition

6.4.3.1. Participant Disposition

All randomized participants will be included in the disposition summaries. Summaries will be displayed by study intervention group for participants 18 through 64 years of age.

The number of randomized participants will be included in the participant disposition summary. In addition, the number and percentage of participants who received vaccinations, completed the follow-up visits, and withdrew from the study, along with the reasons for withdrawal, will be tabulated by study intervention group.

Participants excluded from each analysis population will also be summarized by study intervention group and age stratum separately along with the reasons for exclusion (eg, for the evaluable immunogenicity population).

6.4.3.2. Blood Samples for Assay

For each blood sampling time point, the number and percentage of randomized participants providing blood samples within the protocol-specified time frame, as well as before and after the protocol-specified time frame, will be tabulated by study intervention group for participants 18 through 64 years of age.

6.4.3.3. E-Diaries

E-diary compliance as defined in Section 3.4.1 will be summarized using descriptive statistics. The safety population will be used to generate the summary reports. The denominator for the e-diary compliance rates will be the total number of participants who received the specific vaccination.

6.4.4. Study Intervention Exposure

The number and percentage of participants randomized and receiving each study intervention will be tabulated by study intervention group for all randomized participants 18 through 64 years of age. In addition, the relation of the randomized study intervention to the actual study intervention received will be presented as a cross-tabulation of the actual study intervention received versus the randomized study intervention for participants 18 through 64 years of age.

6.5. Safety Summaries and Analyses

The data collected for study participants who report any symptom(s) that might be indicative of myocarditis or pericarditis within 4 weeks after a study vaccination (ECG, troponin level, cardiac echocardiogram, and/or cardiac magnetic resonance study) will be summarized and listed by study intervention.

6.5.1. Adverse Events

The planned analyses for AEs and SAEs are outlined in Section 6.1.2.

6.5.2. Laboratory Data

The planned analyses for laboratory data are outlined in Section 6.1.3.

6.5.3. Electrocardiograms

The planned analyses for ECGs are outlined in Section 6.1.4.

7. INTERIM ANALYSES

7.1. Introduction

This study will use an IRC, an internal Pfizer committee that will review data. The IRC is independent of the study team and includes only internal members. The IRC charter describes the role of the IRC in more detail.

Statistical analyses will be carried out when the final data for specified objectives are available while the study is ongoing. The timing of these planned analysis and reporting events is described in Section 7.1.1 below.

